12.0 STUDY TERMINATION/SUBJECT WITHDRAWAL

12.1 Study Termination

This study may be terminated for the following reasons:

- Discovery of unforeseen risk that could jeopardize the dental/physical well-being of subjects
- Enrollment or recall rates those are not likely to produce sufficient data for evaluation of safety and efficacy
- Non-compliance with the study protocol, the Investigator Agreement, applicable FDA regulations or conditions of approval imposed by the reviewing IRB
- Withdrawal of IRB approval

In the event of study termination, the Principal Investigator will determine whether subjects are in need of additional treatment and/or follow-up observation as a result of participation in this trial.

APPENDIX 1: FITTING

FITTING	
A=	Good natural retention
B=	Moderate natural retention
C=	Little or no natural retention

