7.5.3 Crown Fitting, Adjustment and Cementation

A) For NuSmile PVSCC Signature Crowns:

In some cases, shortening the crown from the gingival margin may be necessary to achieve the desired results. The NuSmile Shortening Bur may be used at low range speed with a water spray to circumferentially reduce and feather the crown margins. After shortening, the composite polisher may be used to restore a polished surface to the esthetic facing.

A properly fitted crown will have a passive fit and be seated with finger pressure only. A "snap fit" is both undesirable and counter-productive as it may result in failure of the veneer. If the crown does not fit passively, the preparation must be refined to fit the crown. Crimping is not necessary, but if needed, excessive crimping or crimping near the facing must be avoided.

Clean the teeth of saliva, blood or debris and control gingival hemorrhage. NuSmile's Bio-active Resin Modified Glass Ionomer Cement will be used to cement the crowns according to the manufacturer's directions for use.

Once seated and after allowing enough time for the cement to set, a white stone or composite finishing bur may be used to equilibrate the veneer out of excessive occlusal contact in centric and excursion functions. The opposing teeth may be slightly adjusted, if needed.

It may be desirable to trim the veneer flush with the incisal edge if the patient demonstrates bruxism patterns or end-on occlusion. The distal point angle may be rounded to shape the crown for a right or left anterior.

B) For NuSmile *ZR* crowns:

Use NuSmile *Try-In* Crowns to test the fit and to avoid contamination with saliva or blood of NuSmile *ZR* Crown's prepared internal surface. If contamination with saliva or blood occurs, clean the internal surface of the NuSmile *ZR* Crown with Ivoclean or sandblast with aluminum oxide.

A properly fitted crown will have a passive fit and be seated with finger pressure only. A "snap fit" is both undesirable and counter-productive as it may result in fracture of the crown. If the crown does not fit passively, the preparation must be refined to fit the crown.

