10. STUDY ASSESSMENTS

Clinical Assessments will be done at baseline post crown placement; at months 3, 6, 12 and 18; and end of study visit occurring in range of 24 to 30 months from baseline.

Assessments and documentation required at each assessment interval:

• Photographs of selected teeth	Baseline
• Photographs of tooth preparations	Baseline and when possible
• Photographs of cemented crowns	Baseline
• Photographs of occlusal and frontal views	Baseline and when possible
• Assessment of fit	All intervals
• Assessment of positioning	All intervals
• Assessment of proximal contact	All intervals
• Assessment of marginal adaptation	All intervals
• Assessment of color: match , staining/color change	All intervals
• Assessment of time placement	Baseline
• Assessment of gingival status	All intervals
• Assessment of retention	3, 6, 12, 18 and 24 mo
• Assessment of veneer/composite integrity	3, 6, 12, 18 and 24 mo
• Assessment of secondary caries	3, 6, 12, 18 and 24 mo
• Assessment of trauma	3, 6, 12, 18 and 24 mo
• Assessment of clinical pulp pathology	3, 6, 12, 18 and 24 mo
• Assessment of radiographic pulp pathology	24 mo
• Assessment of tooth	All intervals
• Assessment of parents' esthetic satisfaction	All intervals (baseline at 3-month follow up)

Non-recall assessment to be done at the time of tooth/crown lost to study due to trauma. If this was to occur, the patient would be discontinued from study and the justification recorded.

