11.0 DATA ANALYSIS

Descriptive statistics (means, standard deviations, counts, and percentages) will be calculated for all variables. To evaluate if the primary efficacy variables differ by the three treatment groups (NuSmile PVSCC Signature Crowns, NuSmile ZR, and Strip composite crowns), ANOVA or Chi-square tests of association will be performed.

All subjects evaluated at the 6-month interval or beyond and subjects who have lost crowns or teeth will be considered for efficacy. All enrolled subjects defined here as those who have had at least one crown placed will be evaluated for safety. Any missing, unused or false data will be omitted from data analysis.

The primary efficacy variables in this trial are fit, positioning, proximal contact, marginal adaptation, color match, gingival status, crown retention, veneer/composite integrity, secondary caries, occlusal integrity, history of trauma, clinical pulp pathology, parents' esthetic satisfaction. Scores for efficacy variables will be summarized and displayed using descriptive statistics (means, standard deviations, counts, and percentages).

Inferential statistics will be used to detect significant differences in the primary efficacy variables by the treatment status at baseline and at 6, 12, 18, and 24 month follow-up. Statistical differences will be calculated using logistic regression models accounting for within cluster variance using generalized estimating equations (GEE).

Safety variables include Adverse Events and Unanticipated Adverse Device Effects. All subjects that have had crowns placed will be evaluated for safety. Descriptions of occurrences, incidence, severity and required treatments for Adverse Events and Unanticipated Adverse Device Effects Will be summarized and tabulated where appropriate.

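### Fit, a primary efficacy variable, is graded by an undefined natural retention and scored only after cementation or bonding, so its three-arm comparisons are not like for like

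*Combined protocol and SAP*

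**What the plan says.** Appendix 1 gives Fit three grades: A is "Good natural retention", B is the moderate level, and C is "Little or no natural retention". No section says what natural retention means, and there is no arm-specific rule or not-applicable code.

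Section 10 states that "Clinical Assessments will be done at baseline post crown placement" and at the later visits, and its table puts "Assessment of fit" at all intervals. Section 8 gives the same timing.

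Section 11 opens its list of outcomes with Fit: "The primary efficacy variables in this trial are fit, positioning, proximal contact, marginal adaptation, color match, gingival status", followed by seven more. Inferential statistics are planned for differences in the "primary efficacy variables by the treatment status at baseline and at 6, 12, 18, and 24 month follow-up", with the three treatment groups as the comparison.

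Section 7.5.3 describes placement. For both Signature and ZR crowns, "A properly fitted crown will have a passive fit and be seated with finger pressure only", and a snap fit is called undesirable. Both types are then cemented with a resin-modified glass ionomer. Strip crowns are composite cured onto etched enamel coated with bonding resin, after which the celluloid form is taken off.

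**The concern.** The ordinary meaning of natural retention is the hold a crown has on the prepared tooth without cement. That is a property of a preformed crown before it is fixed, yet all scheduled scores come after fixation. In the control arm there is never an unfixed restoration to grade.

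Examiners following the plan would have to supply their own definition. One might give A to every crown still in place, which would duplicate Appendix 8 (Retention); another might grade something else. A difference in Fit between the composite arm and the preformed arms could then reflect how the scale was applied and not how the crowns performed. No analysis can repair this later, because the uncemented state is gone once the crown is cemented.

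**Working it through.** The plan states no figure that bears on this point, and the sample size is a convenience sample, so there is nothing to reproduce. The check is a reading of the sections side by side, plus counts.

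**1. Timing of the scores against fixation of the crown**

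| Arm | How fixed (7.5.3) | Unfixed restoration available to grade? | First scheduled Fit score (8, 10) |
|---|---|---|---|
| Signature | Cemented | Yes, at try-in | After placement |
| ZR | Cemented | Yes, at try-in (Try-In crowns test the fit) | After placement |
| Strip composite | Cured onto bonded enamel | No | After placement |

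Fit is scheduled at baseline and at months 3, 6, 12, 18 and 24, which is 6 visits. All 6 follow fixation as the schedule is written. The plan itself treats cement as a separate factor: Appendix 8 sorts lost crowns by where cement remains.

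**2. Teeth that could not be fitted**

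Under Section 7.5.4, a tooth that cannot accommodate its assigned crown receives a composite crown and stays in the study under intention-to-treat. The clearest fit failures in the preformed arms would therefore be graded on a composite restoration, for which the scale has no evident meaning.

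**3. The scale against the placement text**

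Section 7.5.3 sets passive seating as the mark of a proper fit in the preformed arms. Appendix 1 puts strong natural hold at the top of the scale. If natural retention means hold without cement, the two sit uneasily together.

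**4. Extent**

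- Named primary efficacy variables in Section 11, grouped here by kind: 5 on seating and appearance (fit, positioning, proximal contact, marginal adaptation, color match); 3 on durability (crown retention, veneer/composite integrity, occlusal integrity); 4 on tissue and disease (gingival status, secondary caries, clinical pulp pathology, trauma history); and 1 from the parents (esthetic satisfaction). 5 + 3 + 4 + 1 = 13.
- Inferential time points: baseline, 6, 12, 18, 24 months = 5. Month 3 is assessed but not listed for inference.
- Nominal grid of variable-by-time comparisons: 13 × 5 = 65. Fit accounts for 1 × 5 = 5 of them (5/65 = 1/13, about 8%). The grid is nominal because Section 10 starts some variables only at month 3.

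**5. Cross-references**

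Section 8 points to Appendix 3 for all scoring, but that appendix is Proximal Contact. Section 7.5.4 points to Appendix 2 for the reason for fitting failure, but that is Positioning. Fit is tied to Appendix 1 only by the appendix title.

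**The case against.** The strongest reply is that the difficulty depends on a definition the reader supplies. Appendix 1 does not say that natural retention means hold without cement, and nowhere do the documents say it cannot be judged after cementation. This stands as a limit on the claim, but it does not rescue the variable: an undefined primary outcome is no better a basis for a three-arm test.

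A reader might infer that the scale penalises correctly placed crowns in all 60 of the 90 children in the Signature and ZR arms. The documents do not establish that. Passive seating describes how a crown goes on, not how much hold it has once seated, and Section 7.5.3 allows limited crimping of Signature crowns if needed, so some mechanical hold is compatible with it. A conflict is likely but not proven, and 60 is only 30 + 30, the size of two arms.

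A reader might also infer that fit problems go unrecorded altogether. They do not. Appendix 4 grades marginal discrepancies up to replacement required, Appendices 2 and 3 grade position and proximal contact, and Section 7.5.4 requires the reason for a fitting failure to be recorded. The wrong appendix number there looks like a numbering slip.

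Finally, fit in the preformed arms is checked before cementation on the day of placement, so an operator could enter that observation as baseline. This is fair, and it shows the information exists. But the written schedule says after placement, and the argument does not reach the follow-up visits or the strip-crown arm.

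**Conclusion.** The point holds for this one variable. As written, Fit rests on an undefined term, is scored only after cementation or bonding, and has no evident meaning in the control arm, so its 5 planned three-arm comparisons are not like for like. The conclusion assumes that natural retention is meant in its ordinary sense; under another definition the timing problem might ease, but the documents offer none.

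It would go too far to call the efficacy analysis as a whole invalid. Fit is 1 of 13 named primary variables in a pilot, the other 12 are unaffected, and no sample size, success criterion or safety rule depends on it. The change should be made, and before enrolment because the loss is irreversible for each crown once cemented, but the trial does not stand or fall on it.

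**What to change.** - Replace the Appendix 1 grades with defined ones that are consistent with the fit described in Section 7.5.3, and reconcile the two texts.
- Score Fit once, at try-in before cementation, in the Signature and ZR arms. Record teeth where the crown could not be fitted, with the reason, as Section 7.5.4 already asks. Report this descriptively.
- Remove Fit from the 3- to 24-month assessments and from the three-arm tests in Section 11. Hold over time is already covered in all arms by Appendix 8, and adaptation by Appendix 4.
- Correct the appendix references in Sections 7.5.4 and 8 in the same edit.

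The cost is a revised appendix, edited Fit entries in Sections 8, 10 and 11, and one fewer three-arm efficacy variable. No visit or staff is added, and the follow-up form becomes shorter. If the sponsor wants to keep a three-arm variable, the alternative is a defined post-placement fit measure that applies equally to cemented and bonded crowns.

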APPENDIX 2: POSITIONING

POSITIONING	
A=	Proper position
B=	Rotated – in occlusion
C=	Not in occlusion with or without rotation

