6.2 Exclusion Criteria

- Medically compromising condition
- Teeth with proximal space closures of sufficient magnitude to preclude placement of crown
- Teeth with complete absence of facial or lingual walls following tooth preparation
- Teeth that are expected to be exfoliated/extracted within one year will not participate in the study
- Anterior crowding
- Occlusion class III

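### Positioning is graded on rotation and occlusal contact, but neither is scored before treatment or used in the analysis, so B and C rates mix the child's own bite with the crown

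*Combined protocol and SAP*

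**What the plan says.** Section 11.0 opens its list of 13 primary endpoints with "The primary efficacy variables in this trial are fit, positioning, proximal contact, marginal adaptation". In the Section 10 schedule, "Assessment of positioning" falls at every interval, and the first interval comes after treatment: "Clinical Assessments will be done at baseline post crown placement".

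Appendix 2 has three grades. A is a correctly positioned tooth, B is a rotated tooth that occludes, and C is "Not in occlusion with or without rotation". None refers to how the tooth stood before the crown.

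The bite enters the protocol before treatment in two places. Section 6.2 excludes anterior crowding and "Occlusion class III", and Section 7.3 has every subject screened against these criteria before enrollment. Section 10 also lists "Photographs of selected teeth" at baseline, and "Photographs of occlusal and frontal views" at baseline and otherwise as feasible. It does not say whether the occlusal and frontal views precede placement, and nothing in the plan has any photograph graded for contact or rotation.

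Section 7.4 randomizes by patient, 30 per arm, with all of a child's study teeth receiving the same restoration. Section 11.0 compares arms by logistic GEE at baseline and at 6, 12, 18 and 24 months. It gives no cut-point for the A/B/C scale and no covariate for the pre-treatment bite.

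**The concern.** An endpoint meant to show how a crown sits should not depend on whether the child's incisors could ever have met. Anterior open bite and a large overjet are not exclusions. If the incisors do not meet, the tooth is graded C after placement and probably at each later visit, whatever was placed. A tooth that was naturally rotated can likewise be graded B.

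Two things are at stake. The first is the absolute rate of B and C grades in each arm. Descriptive rates are a main product of a pilot, and here they would partly describe the children. The second is the contrast between arms at the post-placement score. Pre-existing cases add the same expected floor to every arm and shrink the visible difference.

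**Working it through.** The plan has no figure to reproduce. Section 5 calls the 90 subjects (3 × 30) a convenience sample and states no alpha, power, effect size or expected rate. What follows is an illustration.

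**Inputs**
- From the documents: 30 children per arm (Sections 5 and 7.4).
- Assumed, because the documents give no value: crown-caused grade C in 5% of one arm and 25% of another; share *m* of children out of contact before treatment, from 0 to 30%; C compared with A or B; one tooth per child; two-sided 5% test.

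**Formulas**
- Observed C rate = *m* + (1 − *m*)*p*, where *p* is the crown-caused rate.
- Observed difference = (1 − *m*)(0.25 − 0.05).
- SD of the chance difference in *m* between two arms = √(2*m*(1 − *m*)/30).
- Power: exact binomial enumeration of the pooled z-test, 30 per arm.

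**Worked case, *m* = 10%**
- Rates: 0.10 + 0.90 × 0.05 = 14.5%, and 0.10 + 0.90 × 0.25 = 32.5%.
- Odds ratio: (0.325/0.675)/(0.145/0.855) = 2.8.
- Chance imbalance SD: √(2 × 0.10 × 0.90/30) = 7.7 points.
- Share of C grades in the better arm that were there before treatment: 0.10/0.145 = 69%.

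| *m* | Observed C rates | Difference (points) | Odds ratio | Power | SD of chance imbalance (points) |
|---|---|---|---|---|---|
| 0 | 5.0% vs 25.0% | 20.0 | 6.3 | 63% | 0 |
| 2% | 6.9% vs 26.5% | 19.6 | 4.9 | 56% | 3.6 |
| 5% | 9.75% vs 28.75% | 19.0 | 3.7 | 47% | 5.6 |
| 10% | 14.5% vs 32.5% | 18.0 | 2.8 | 38% | 7.7 |
| 20% | 24.0% vs 40.0% | 16.0 | 2.1 | 26% | 10.3 |
| 30% | 33.5% vs 47.5% | 14.0 | 1.8 | 19% | 11.8 |

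**No true difference.** If *p* is the same in both arms, the observed rates are the same and the expected difference is 0 at every *m*.

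**Other crown-caused rates.** With 5% and 30% assumed instead, a standard two-proportion calculation gives power of 73%, 51% and 37% at *m* = 0, 10% and 20%, so the pattern is the same.

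**What a pre-treatment record would recover.** Restricting the comparison to children with possible contact leaves 30 × 0.90 = 27 per arm at *m* = 10%, and 30 × 0.80 = 24 at *m* = 20%. The contrast is again 5% vs 25%, and power is about 59% and 53%, against 38% and 26% without the record.

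**The case against.** The strongest reply is that the trial is randomized by patient, so pre-existing malocclusion is balanced in expectation and cannot favor a product. That stands. A reader might infer from Appendix 2 that the arm comparison is biased, and the documents do not support this: the expected difference is zero when the crowns do not differ. Dilution, chance imbalance and inflated absolute rates remain.

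A reader might also infer that the bite is never looked at before treatment. That goes too far. Screening for class III and crowding requires looking at it and removes part of the problem, and the photographs of the selected teeth, listed apart from those of preparations and cemented crowns, are plausibly pre-operative. The gap is that contact and rotation are not scored or carried into the analysis.

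The post-placement score does serve as a reference for later change. However, Section 11.0 describes no change analysis, a tooth that starts at C has no lower grade to move to, and at that first score the child's bite and the seating of the crown are already merged.

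Section 7.5.3 could be read as pushing the Signature arm towards grade C, since a stone or bur "may be used to equilibrate the veneer out of excessive occlusal contact in centric and excursion functions". The wording is permissive and concerns only excessive contact. Relieving that is not the same as taking the tooth out of occlusion, so no effect specific to that arm follows.

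Finally, the plan claims no power, so no planned power is lost. It does not define C as failure, so treating C as the worst grade rests on the order of the scale. Section 6 expects 120 to 200 crowns in 90 children, not one each. These points limit what the figures show, but they do not remove the gap in measurement.

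**Conclusion.** The point holds as a modest measurement gap in one of 13 primary variables of a pilot. As written, the plan cannot tell a crown that seats out of occlusion or rotated from a tooth that was already so. The B and C rates are therefore inflated in every arm by an unknown amount, and the post-placement contrast is diluted.

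The size depends on a prevalence the documents do not give. Under the stated assumptions the effect is small at 2% (power 56% against 63%) and substantial at 10% to 20% (38% to 26%), with a chance imbalance SD of 7.7 to 10.3 points between two arms. These figures rest on the assumed 5% and 25% rates, a C versus A/B split and one tooth per child, and are illustrative only. They do not support a claim of systematic bias between arms or of a shortfall against a power target, because the plan sets none.

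**What to change.** At the existing screening, before allocation, record for each child whether the incisors meet and for each study tooth whether it is rotated. In Section 10, state that the baseline occlusal and frontal photographs are taken pre-operatively.

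In Section 11.0, adjust the positioning GEE model for this record, or report positioning separately for teeth with no pre-treatment contact. If every such tooth scores C, a logistic coefficient for contact cannot be estimated, and separate reporting is then the workable choice. The same section should state how A/B/C is split for the logistic model.

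Keep the Appendix 2 scale as it is. Splitting it into two items would add an outcome to a primary list that already has 13.

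The cost is two tick boxes, one covariate or one extra table, and a few sentences of text. The record will be imperfect where decay has already removed tooth structure, because contact lost to caries may look like a bite in which the incisors never met.

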APPENDIX 3: PROXIMAL CONTACT

PROXIMAL CONTACT	
A=	Open spaces
B=	Floss meets little or no resistance when passes through contact
C=	Floss meets significant when passes through contact

APPENDIX 4: MARGINAL ADAPTATION

MARGINAL ADAPTATION	
A=	No discrepancies detected with explorer
B=	Detectable discrepancies but clinically acceptable
C=	Detectable discrepancies, not acceptable –replacement required

APPENDIX 5: COLOR: MATCH, STAINING/COLOR CHANGE

COLOR: MATCH, STAINING/COLOR CHANGE	
A=	Matches structure
B=	Does not completely match but within range of shade and translucency
C1=	Outside range with yellow to yellow/brown discoloration
C2=	Outside range with light gray to dark gray discoloration
C3=	Outside range for reason other than yellowing or graying

